## I. OVERVIEW

### 1. Background

**Background:** Hereditary cancer syndromes cause a high lifetime risk of early, aggressive cancers. Early recognition of individuals at risk can allow risk-reducing interventions that improve morbidity and mortality. Family health history applications that gather data directly from patients could alleviate barriers to risk assessment in the clinical appointment, such as lack of provider knowledge of genetics guidelines and limited time in the clinical appointment. New approaches allow linking these applications to patient health portals and their electronic health records (EHRs), offering an end-to-end solution for patient-input family history information and risk result clinical decision support for their provider.

**Methods:** We describe the design of the first large-scale evaluation of an EHR-integrable, patient-facing family history software platform based on the Substitutable Medical Applications and Reusable Technologies on Fast Healthcare Interoperability Resources (SMART on FHIR) standard. In our study, we leverage an established implementation science framework to evaluate the success of our model to facilitate scalable, systematic risk assessment for hereditary cancers in diverse clinical environments in a large pragmatic study at two sites.

**Conclusions:** Our research study will provide evidence regarding a new care delivery model that is scalable and sustainable for a variety of medical centers and clinics.

## II. GOALS AND POPULATION

### 2. Analytic Goals

- a. **Aim 1:** Deploy a care delivery model that will facilitate systemic risk assessment for hereditary cancers in diverse clinical environments.
- b. **Research Question:** What proportion of enrolled individuals complete the MeTree questionnaire?

### 3. Analytical Population(s)

- a. **Reach population:** defined as the participants who were invited to use MeTree (completed baseline surveys and clicked link to use MeTree)
- b. **Effectiveness population:** defined as the participants who completed MeTree and had a clinical decision support risk report generated.
- c. **Genetic counseling population:** The genetic counseling population includes participants who completed MeTree, received a genetic counseling recommendation and completed the genetic counseling appointment. A random selection of non-study participants with genetic counseling appointments at the same clinic and in the same time frame will be selected, 1:1.
- d. See the protocol paper for additional details of these populations:  
<https://www.sciencedirect.com/science/article/pii/S1551714424002970#f0010>
- e. Study participants had to meet the following inclusion and exclusion criteria to be enrolled in the FOREST study:
  - i. Inclusion
    1. Site: VUMC, MMC
    2. Demographics: Age 18 years or older
    3. Able to read and communicate in English
    4. Willing and able to use the internet to report FHH information
    5. Current user of patient portal (VUMC specific)
  - ii. Exclusion
    1. Not a patient at VUMC or MMC sites
    2. Diagnosed with a terminal illness
    3. Unable to speak/read English
    4. Unwilling or unable to use the Internet to report their FHH information
    5. Report previous genetic testing and/or counseling through the VUMC Hereditary Cancer Clinic
- f. Analyses involving EHR -related information will be restricted to VUMC participants due to the specificity of the EHR-based outcomes.

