If a patient clicks, I'm Interested, the REDCap Participant Updater Module will create a record in the study database that includes patient MRN and the enrollment status of Interested. Once the Updater Module creates a new record, it will trigger REDCap to fetch the email address to facilitate sending the follow-up email from REDCap, which will include more information about the study and a link to the survey.

[name]
U01-CA232829-01A1
FOREST

If a patient clicks, No, Thank You, the REDCap Participant Updater Module will create a record in the study database that includes patient MRN and the enrollment status of Not Interested. This will prevent any further communication to the patient about this study.

Once the eligible participant enters the REDCap study pre-screen, they will be able to complete the eligibility survey, electronic consent, and pre-MeTree survey. At the end of the pre-MeTree survey, participants will be given a link to the MeTree platform to begin the questionnaire. At any time, they can leave MeTree and re-enter by using the link from the REDCap message or by the link in their MHAV portal. Participants will receive a \$10 gift card for completing the eligibility, eConsent, and pre-MeTree surveys.

After completing the eligibility, eConsent, and pre-MeTree surveys, participants will receive an email with the link to MeTree (**Appendix K**). Participants have three weeks to complete their MeTree questionnaire. After completing the questionnaire, participants will receive a report from MeTree. After receiving the report from MeTree, and once the study team has concluded the enrollment of the 3,500 participants, 300 “high risk” participants will be referred to the Hereditary Cancer Clinic to discuss their results with a Genetic Counselor. The consent will include information about this step to inform participants that they may be contacted for counseling.

*My Health at Vanderbilt (MHAV) language is used to describe the workflow at Vanderbilt.

5. Study Procedures

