## IV. STATISTICAL ANALYSIS

### 1. Analysis Objectives and Tasks

- a. Describe the Reach populations

- i. **Analysis:** Descriptive statistics (counts and percentages, mean, median, standard deviation, IQR range) will be used to describe the demographics and baseline characteristics of the **Reach population**. Statistical tests: fisher's exact test, chi-square test, or wilcoxon ranked sum test will be used to identify differences between the participants who completed MeTree (Effectiveness population) and did not complete MeTree within the Reach population

- b. Describe the genetic counseling populations

- i. **Analysis:** Descriptive statistics (mean, standard deviation, median and IQR or counts and percentages) will be used to describe differences in demographics by intervention group, MeTree and standard of care. Difference between groups will be assed via Wilcox rank sum test or fisher's exact test.

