### 2. Primary Endpoint: Completion of MeTree

- a. Implementation endpoint: Report the number and percentage of participants who completed MeTree out of the reach population. As single-arm implementation endpoint, no inferential statistics will be used.

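### The SAP asks what share of enrolled people complete MeTree, but its primary percentage leaves out enrolled people who never clicked the MeTree link

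*SAP*

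**What the plan says.** SAP II.2.b sets the research question for Aim 1: "What proportion of enrolled individuals complete the MeTree questionnaire". SAP IV.2 then defines what will be reported for the primary endpoint: "Report the number and percentage of participants who completed MeTree out of the reach population". It adds that no inferential statistics will be used. SAP II.3.a describes Reach as "defined as the participants who were invited to use MeTree (completed baseline surveys and clicked link to use MeTree". For further detail on the populations, SAP II.3.d refers to a published paper that is not among the documents.

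The protocol gives the order of events:

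- Section 4: eligibility survey, electronic consent and baseline survey come first. Then "At the end of the pre-MeTree survey, participants will be given a link to the MeTree platform to begin the questionnaire". An email carrying the link follows.
- Section 5: people are asked to complete MeTree once they are enrolled. Vanderbilt participants who have not accessed it 30 days after consent get weekly reminders for up to four weeks.
- Section 7, on non-responders: people who enrol but do not complete MeTree are still classed as enrolled, and also as excluded.

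Neither document defines 'enrolled'. Protocol section 4 even uses the word before consent: a click on the interest button will "create a record in the study database that includes patient MRN and the enrollment status of Interested".

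**The concern.** The question and the percentage meant to answer it have different denominators. Reach has two entry conditions, finishing the baseline surveys and clicking the link. In the protocol's sequence the click comes after enrolment, and the reminder scheme shows that some consented people are expected not to have accessed MeTree. Someone who enrols and never clicks has not completed MeTree, but is missing from the percentage instead of counting against it.

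The primary endpoint is a single number and percentage, so the choice of denominator decides what it means. The SAP plans no completion percentage over all enrolled. Its comparison of completers with non-completers (SAP IV.1.a) is also made within Reach, so people lost between enrolment and first access would not be described there either. For a study meant to show that a care delivery model is scalable, that loss is part of the evidence.

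**Working it through.** **The plan's own figure.** The documents give no expected completion rate and no click rate. The one figure that counts completers is in Protocol section 8: 150 high-risk patients seen, 10% identified, 50% follow-up. 150 / (0.10 × 0.50) = 3,000, which matches the stated minimum. It does not settle which denominator applies.

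**Who leaves the denominator, by reading.**

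| Enrolment is reached at | Reach read as | Enrolled people outside Reach |
|---|---|---|
| Consent | clicked the link | those who did not finish the baseline surveys, and those who finished but never clicked |
| Consent | sent the link | those who did not finish the baseline surveys |
| End of baseline survey | clicked the link | those who never clicked |
| End of baseline survey | sent the link | none, if everyone who finishes is sent the link |

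**Formula.** Let c = Reach / enrolled, and let r_in and r_out be the completion proportions inside and outside Reach.

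- Reported proportion = r_in.
- Completion among the enrolled: E = c × r_in + (1 − c) × r_out.
- The reported figure exceeds E exactly when c < 1 and r_out < r_in.
- With all completers inside Reach, r_out = 0, so E = c × r_in and reported / E = 1/c = enrolled / Reach.

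The SAP points to r_out = 0. SAP IV.1.a compares "participants who completed MeTree (Effectiveness population) and did not complete MeTree within the Reach population", which treats the completers as a subset of Reach.

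**Illustration with assumed c and an assumed reported 75%.**

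| c | 1/c | Completion among the enrolled |
|---|---|---|
| 0.98 | 1.02 | 0.75 × 0.98 = 73.5% |
| 0.95 | 1.05 | 0.75 × 0.95 = 71.3% |
| 0.90 | 1.11 | 0.75 × 0.90 = 67.5% |

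**The same in counts (assumed).** Take 1,000 enrolled, 900 in Reach and 675 completers in Reach.

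- Of Reach: 675/900 = 75.0%.
- Of the enrolled: 675/1,000 = 67.5%.
- If 25 of the 100 outside Reach also completed but were not counted: (675 + 25)/1,000 = 70.0%.
- The gap closes only if 75 of those 100 completed: (675 + 75)/1,000 = 75.0%.

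**At the planned scale.** With 3,500 enrolled and 3,000 completers, completion among the enrolled is 3,000/3,500 = 85.7%. If an assumed 5% of the enrolled were outside Reach, the reported figure would be 3,000/3,325 = 90.2%. At 10% it would be 3,000/3,150 = 95.2%.

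**The case against.** The strongest reply is that the gap may not exist. The parenthesis in the Reach definition can be read as explaining 'invited', with the click serving only as a marker that the link was sent. If enrolment also ends with the baseline survey, Reach and enrolled coincide. The cited paper might confirm this. The point stands as a possibility, and for that reason the documents do not support saying flatly that the percentage fails to answer the question. They also do not rule the gap out: the SAP's words require a click, the protocol separates receiving the link from using it, and 'enrolled' is left open.

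A second reply is that completion among people who reached the tool is a legitimate implementation measure, openly defined, with no inference attached. That is fair. It argues for keeping the Reach percentage, but that percentage does not describe all who enrolled. The reminders, and the lack of any deadline for the click in the Reach definition, may also keep the excluded group small.

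Four stronger readings are tempting and should not be drawn:

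- A reader might infer from SAP II.3.e ("Study participants had to meet the following inclusion and exclusion criteria to be enrolled in the FOREST study") that the groups must differ, because neither the surveys nor the click is listed there. Those are necessary eligibility criteria, not a definition of enrolment; consent is not listed either.
- A reader might infer that several links compete as the first click. Protocol section 4 says participants can leave MeTree and "re-enter by using the link from the REDCap message or by the link in their MHAV portal", so the portal link is described only for returning.
- A reader might infer that everyone at both sites is emailed the link. That text describes the Vanderbilt workflow. Section 5 allows for on-site participation at Meharry and for enrolment by paper, tablet or phone.
- A reader might infer that all non-completers vanish from the denominator. Those who clicked and did not finish stay in Reach.

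**Conclusion.** The mismatch is in the current text: the question is about the enrolled, and the primary percentage is about Reach. Following the SAP as written can overstate completion among the enrolled, and nothing else planned would reveal it. If all completers are inside Reach, the direction is upward or nil, by the factor enrolled/Reach. If some people outside Reach also complete, the overstatement persists as long as they do so less often than those inside.

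The size cannot be found from the documents. It depends on an undefined term and an unreported click rate, and it may be small or zero. The conclusion is therefore that the denominator needs to be settled, not that a material error has been shown. The point is worth fixing because it concerns the SAP's primary endpoint and the repair is cheap.

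**What to change.** In the SAP:

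1. Define 'enrolled', for example as eligible and consented.
2. Report completion over all enrolled as the percentage that answers II.2.b.
3. Keep completion within Reach as a separately labelled figure.
4. State in II.3.a whether Reach means sent the link or clicked it. If a click is only a marker of being sent the link, say so.
5. Show the counts consented, baseline complete, link clicked and MeTree completed.
6. Reconcile this with Protocol section 7, which classes non-completers as both enrolled and excluded, so that they are not removed from the new denominator.

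Rewording II.2.b to match Reach would restore consistency, but completion among the enrolled would still go unreported.

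The cost is SAP wording and one flow table. Consent date already divides the EHR periods (SAP III.2.a.iii), completion is already logged (SAP III.1.a), and Reach as worded already needs click data. The downside is a possibly less favourable headline percentage.

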SA3. Explore the feasibility of our care delivery model to improve family engagement for cancer risk assessment

- Participants extend invitations to family members to MeTree's family resource center to share results of genetic tests
- Assist with education and referral needed for cascade testing for pathogenic variants

3. Inclusion/Exclusion Criteria

Inclusion

- Receiving medical care at Vanderbilt University Medical Center or Meharry Medical College
- Age 18 years or older
- Able to read and communicate in English
- Willing to use the Internet
- Current My Health at Vanderbilt (MHAV) user or willing to sign up and use (Vanderbilt participant requirement only)

Exclusion

- Non-VUMC/MMC patients
- Diagnosed with a terminal illness
- Unable to speak/read English
- Unable/unwilling to use the Internet (specifically MeTree)
- Previous genetic testing and/or counseling through the Hereditary Cancer Clinic

4. Enrollment

Participants will enroll through My Health at Vanderbilt (MHAV)*. MHAV is VUMC's patient portal where the patient may sign up and participate in managing his/her health care. MHAV can also be used for sending mass research recruitment messages to a predefined cohort of patients who meet certain study-specific inclusion/exclusion criteria, have explicitly said OK to Contact for research purposes, and have an active MHAV account. The messaging process is managed centrally by the VICTR/Health IT teams, sending the messages on behalf of the study team.

MHAV: Initial e-mail notification the patient receives about the research study invitation

1. If patients have email notifications turned on, they will receive the standard, system-generated email stating they have a research invitation.

"You have a new message in My Health at Vanderbilt! Please sign in to read your message.
Thanks for using My Health at Vanderbilt,
Vanderbilt University Medical Center"
2. Once a patient logs in, they will be taken to the research studies dashboard and will see the following patient-friendly study title and description under the heading "Studies you may be able to join".

Once a patient clicks on the link from the email/text notification or from the MHAV homepage, he/she will be taken to the Research Studies page. Here the new study will be listed under the heading – Studies you may be able to join – with the following information (**Appendix H**):

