## 2. Secondary outcomes derivations and definitions

- a. EHR-based indication for increased cancer risk, defined separate for the time periods

- i. EHR-based variables
  - 1. Variable 1: Personal history code in EHR [Yes/No]
  - 2. Variable 2: Family history code in EHR [Yes/No]
  - 3. Variable 3: Other code in EHR [Yes/No]
- ii. Derived outcomes from the EHR-based variables
  - 1. Variable 4: number of Variables 1-3 with value = Yes
  - 2. Variable 5: at least 1 of Variables 1-3 is Yes
  - 3. Variable 6: number of Variables 1 and 2 with value = Yes
  - 4. Variable 7: at least 1 of Variables 1 and 2 is Yes
- iii. Each of the variables above are defined for two time periods
  - 1. T0 - T1 = before consent through date of consent into the study
  - 2. T1 - T2 = after consent through the end of the study
- iv. Endpoint: Variable 7, at least one of personal history code or family history code, Variables 1 and 2 respectively, are met
- v. Sensitivity Endpoints:
  - 1. Variable 1: Personal history code in EHR
  - 2. Variable 2: Family history code in EHR

- b. Genetic counseling appointment times

- i. Length of genetic counseling appointments

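### Controls for the appointment-length comparison are not limited to first visits, and the analysed appointment is not defined in either group (SAP II.3.c, III.2.b)

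*SAP*

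**What the plan says.** SAP II.3.c forms the two groups compared in Secondary Endpoint 2. The MeTree group is made up of people who finished MeTree, were recommended counseling and "completed the genetic counseling appointment". The control rule is: "A random selection of non-study participants with genetic counseling appointments at the same clinic and in the same time frame will be selected, 1:1". It fixes study status, clinic, time frame and ratio. It does not mention visit type or previous contact with the clinic.

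The eligibility list in SAP II.3.e opens with "Study participants had to meet the following inclusion and exclusion criteria to be enrolled in the FOREST study", and one of its exclusions is "Report previous genetic testing and/or counseling through the VUMC Hereditary Cancer Clinic". Protocol section 3 has the matching exclusion: "Previous genetic testing and/or counseling through the Hereditary Cancer Clinic". Both govern enrollment in FOREST, and controls are by definition not enrolled.

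The outcome in SAP III.2.b is given only as "Length of genetic counseling appointments". Protocol section 5 plans to record how many appointments take place as well as how long they last. It describes the comparators as routine patients, picked by the study team for retrospective review of time in clinic. SAP IV.4 compares the groups with a Wilcoxon rank sum test without adjustment. SAP IV.1.b says that summary statistics "will be used to describe differences in demographics by intervention group, MeTree and standard of care". SAP II.3.d adds: "See the protocol paper for additional details of these populations". That paper is not among the documents reviewed.

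**The concern.** The comparison is meant to show whether a family history recorded beforehand changes the length of a counseling appointment. The natural counterfactual for a participant is a patient who is equally new to the clinic but has not used MeTree. Random sampling from all counseling appointments makes controls representative of the clinic's workload. It does not make them comparable with participants, who were screened for no previous testing or counseling there.

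If return visits enter the control group and differ in length from first visits, the test picks up visit type as well as MeTree. Shorter return visits among controls would hide a real saving or make MeTree appear slower. Longer ones would produce an apparent saving. The planned group description covers demographics only, so the imbalance would not be seen.

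**Working it through.** **The plan's own figure.** Protocol section 8 needs 150 high-risk MeTree completers to see a counselor, with 10% identified and 50% attending: 150 / (0.10 × 0.50) = 3,000 completers. This reproduces the stated minimum. The 150 itself cannot be reproduced, because no effect size, SD, alpha or power is given for it. For scale, at 150 per group and two-sided 0.05, the normal formula gives a detectable difference of (1.960 + 0.842) × √(2/150) = 0.32 SD at 80% power and 0.37 SD at 90%.

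**Size of the bias in general.** Let r_C and r_M be the shares of return visits among controls and participants, and let L_R and L_F be the mean lengths of return and first visits, taken as the same in both groups. With no MeTree effect:

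difference in means (MeTree minus control) = −(r_C − r_M) × (L_R − L_F)

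This is zero if the shares are equal or the lengths are equal. The documents give none of these four quantities.

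**Illustration (all lengths, SDs and shares are assumptions).** First visits are normal with mean 60 and SD 15 minutes. Return visits occur among controls only (r_M = 0) and have SD 10, or SD 15 in the equal-length row. There are 150 per group, from the protocol's 150 and the SAP's 1:1 ratio. The test is a two-sided Wilcoxon at 0.05, with 5,000 simulated trials per cell. The mean control length shifts by r_C × (L_R − 60); for example, 0.10 × (45 − 60) = −1.5 minutes.

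| Return-visit mean (min) | Shift in control mean at 5 / 10 / 20% share (min) | No true effect: significant result in the direction of the bias | True 6-min saving: power |
|---|---|---|---|
| none | 0 | 2.6% | 91.8% |
| 30 | −1.5 / −3.0 / −6.0 | MeTree longer: 10.4 / 26.8 / 78.4% | 73.2 / 42.1 / 3.7% |
| 45 | −0.75 / −1.5 / −3.0 | MeTree longer: 6.2 / 14.3 / 42.5% | 82.2 / 68.2 / 33.0% |
| 54 | −0.3 / −0.6 / −1.2 | MeTree longer: 4.4 / 6.1 / 12.0% | 89.3 / 85.7 / 75.8% |
| 60 (equal) | 0 | MeTree longer: 2.3 / 2.4 / 2.4% | 92.7 / 92.2 / 92.6% |
| 75 | +0.75 / +1.5 / +3.0 | MeTree shorter: 6.2 / 13.9 / 42.7% | 96.6 / 98.8 / 99.9% (inflated) |

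The nominal one-directional rate is 2.5%. With shorter return visits and a true 10-minute saving, power is at least 96.7% in every cell except one: 56.9% at a 20% share of 30-minute visits. For a 15-minute saving it is at least 99.6% throughout.

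A separate simulation in SD units (4,000 runs per setting) points the same way. With no effect and return visits 1 SD shorter, the two-sided test rejects in about 13% of trials at a 10% share and 35% at a 20% share, instead of 5%.

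**The case against.** The strongest reply is that SAP II.3.c does not claim to be complete. II.3.d sends the reader to a protocol paper for more detail on the populations, and that paper may already restrict controls. This stands. What can be shown is that neither document states such a rule and that the SAP, followed literally, permits return visits.

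Second, the contrast between the groups is not absolute. The participant exclusion applies at enrollment, and in the SAP it rests on self-report. Protocol section 4 places referral after enrollment of the 3,500 has ended, so a participant could attend the clinic in between. Protocol section 5 foresees more than one appointment per person. This also stands. It means that the analysed visit needs defining in both groups, and that the table, with return visits only among controls, shows the most lopsided case. Return visits among participants too would shrink the bias and could reverse it.

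Third, the stated aim of saving family history collection suggests that the investigators have intake visits in mind. That is a fair inference, but it is not a sampling rule.

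A reader might infer that controls do include many return visits and that the endpoint is therefore biased against MeTree. The documents do not support this. They give no visit lengths and no return share, and the direction reverses if return visits are longer.

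**Conclusion.** The point holds as a gap in the sampling rule and in the outcome definition. Carrying out SAP II.3.c exactly as written can place return visits in the control group while participants are mostly new to the clinic, and III.2.b does not say which appointment counts for anyone. Neither the test in IV.4 nor the description in IV.1.b would correct or reveal the imbalance.

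The size and direction are unknown. On the assumed inputs, the consequences run from none (no return visits, or equal length) to serious (a 20% share of half-length return visits). A large true saving would usually still be detected. Only Secondary Endpoint 2 is affected; the primary endpoint and the EHR-based endpoint do not use this comparison. The conclusion is conditional on the cited protocol paper not already containing a control restriction.

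**What to change.** 1. Check the cited protocol paper. If it restricts controls by visit type or previous contact, state that rule in the SAP.
2. If it does not, amend SAP II.3.c so that the random 1:1 control sample is drawn from non-study patients whose sampled appointment is their first genetic counseling visit at that clinic, with no previous testing or counseling there.
3. In SAP III.2.b, define the analysed appointment as the first genetic counseling visit in both groups; for participants, the first after MeTree completion.
4. Confirm that the control chart review in Protocol section 5 captures visit type, since it is described there as limited to time in clinic.
5. Keep the Wilcoxon test.

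The cost is a few sentences of SAP text, a somewhat smaller control pool and a slightly wider chart review of non-participants. One small difference would remain: previous contact is self-reported by participants but would be read from records for controls. That can be stated as a limitation.
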